10.3 SAFETY VARIABLES

- Concomitant medication
- Adverse events

10.3.1 Concomitant medication

Number and percent of patients with concomitant medications will be presented as a frequency arrays by ATC (3 and 5 levels) and treatment groups.

10.3.2 Adverse events and serious adverse events assessment

All adverse events will be coded with MedDRA dictionary (last available version at the moment of coding).

Before the start of statistical analysis all AEs will be qualified as TESS (AEs started after the first study drug dose or worsening conditions for previously available AEs) and not TESS. In case of missing dates in AE reporting dates will be replaced as described in section 7.

Adverse events of the study time (TESS) will be presented by frequencies (number of patients with AEs and number of events) grouped by treatment, System Organ Class (SOC) and Preferred terms (PT) and relation to the study drug and severity.

All AEs (TESS and not TESS) will be presented in listings.

Serious adverse events will be presented separated from all AEs with tables and listings.

11. AGREEMENTS

Statistical analysis will be performed using SAS 9.4 (www.sas.com).

11.1 DESCRIPTIVE STATISTICS

If there were no special cases all continuous data will be presented with a descriptive statistic by treatment group and other subgroups if necessary (time points/visits, for example). There will be presented a number of non-missing values, mean value with a standard deviation, median, minimum and maximum values, p-value of the normality test (Shapiro-Wilk). All values except p-value will be presented with one significant digit after comma, p-values will be presented with three significant digits or <0.001 (if any).

If there were no special cases all nominal and ordered data will be presented with absolute and relative frequencies (%) by treatment groups and subgroups (visits, for example).

11.2 OTHER

Calculation of time periods will be done relative to the date of the informed consent (IC).

¹ Proc Freq, CMH test, row-mean score difference

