3.1 SCREENING

At Screening after signing the informed consent form, patient's demography, medical history and concomitant medications will be collected, oral cavity will be examined, weight and vital signs will be measured and pregnancy test will be performed for inclusion/exclusion criteria assessment. Screening procedures might take up to 4 days before the scheduled tooth extraction procedure including the actual day of extraction.

On Day 1 the patient will undergo extraction of a molar tooth as indicated for the patient's dental condition. The tooth extraction will be conducted using routine technics and anesthetics (recommended types of anesthesia are provided in section 5.9 Concomitant and rescue therapy of the protocol). After that the patient will stay at the site for treatment of pain syndrome according to the protocol.

Pain intensity will be assessed using VAS within 3 hours after the tooth extraction procedure. Patient's overall assessment will be also recorded. If pain intensity on VAS is above 30 mm and pain relief is required, the patient will be randomized in the study.

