3.2 STUDY TREATMENT

The patients will be assigned to one of two treatment group in 1:1 ratio:

- Group 1. OKITASK® 40 mg – 35 patients
- Group 2. Placebo – 35 patients

The patient will assess pain by VAS at 0' – immediately before study drug dosing.

Upon study drug administration the patients will immediately start two stopwatches. One of them will be stopped once the patient feels first perceptible pain relief; the second one will be stopped once the patient feels the meaningful pain relief.

The patient will stay at the site for 6 hours post-dose for pain and AE assessment. Pain intensity will be assessed by VAS at 5', 10', 15', 30', 45', 60' (1 hour), 90' (1.5 hours), 120' (2 hours), 180' (3 hours), 240' (4 hours), 300' (5 hours), and 360' (6 hours) post-dose.

Pain relief will be assessed by VAS at 5', 10', 15', 30', 45', 60' (1 hour), 90' (1.5 hours), 120' (2 hours), 180' (3 hours), 240' (4 hours), 300' (5 hours), and 360' (6 hours) post-dose.

Patients should mark actual time points of VAS measurement. Deviations from planned time points will not be considered as protocol deviations. Only omitted values will be considered as protocol deviations.

Patients' overall assessment will be performed right before the discharge from the site.

Follow-up phone call to the patient to assess AEs will be performed on Day 3 (48 hours

after the study drug dosing). Any SAE spontaneously reported by the patient within 30 days of dosing will be collected.

Should the patient require rescue medication at any time during 6 hours post-dose, the last VAS measurement and patient's overall assessment will be performed before the rescue medication dosing.

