7.2 ADVERSE EVENTS

Treatment emergency sign and symptom (TESS) will be AEs which started after the first study drug dose. Following rules will be applied (Table 7.2):

Table 7.2 TESS classification algorithm

AE start date			Algorithm
Day	Month	Year	
Missed	Missed	Present	If year \geq year of the first drug dose – TESS
Missed	Missed	Missed	The worst case – TESS
Missed	Present	Missed	The worst case – TESS
Present	Missed	Present	If year \geq year of the first drug dose – TESS
Missed	Present	Present	If month and year \geq date of the first study drug dose (month and year) – TESS
Present	Missed	Missed	The worst case – TESS
Present	Present	Missed	The worst case – TESS
Present	Present	Present	Compare dates of AE and the first study drug dose. In case of dates equality qualification will be performed by the sponsor and investigator (questionable TESS)

All questionable TESS flags will be exported to the MS Excel file and send to the sponsor for resolution.

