Time to REMD – Time to rescue medication will be calculated for each subject and presented using only median value. If the number of subjects will be adequate Kaplan-Meier curve and Log rank test will be used to describe and test treatment profile differences.

Patient's overall assessment – will be described as nominal data (6 hours post-

¹ Data must be sorted!

² CS or HF or UN

³ CRF data

⁴ CRF data

dose). Mann-Whitney¹ test will be applied in order to test differences between treatments response.

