OKITASK [®]	5 minutes	xx	xx.x (xx.x)	xx.x	xx.x	xx.x	xx.x
PLACEBO	5 minutes	xx	xx.x (xx.x)	xx.x	xx.x	xx.x	xx.x
$\mu_T - \mu_R$	95% CI		xx.x [xx.x; xx.x]				
...							
OKITASK [®]	6 hours	xx	xx.x (xx.x)	xx.x	xx.x	xx.x	xx.x
PLACEBO	6 hours	xx	xx.x (xx.x)	xx.x	xx.x	xx.x	xx.x
$\mu_T - \mu_R$	95% CI		xx.x [xx.x; xx.x]				

Figure 12.3 Secondary efficacy. Visual Analogue Scale. Pain Relief profile. ITT population. N = XX

Similar to Figure 12.1

Figure 12.4 Secondary efficacy. Visual Analogue Scale. Difference in Pain Relief means with 95% CI. ITT population. N = XX

Similar to Figure 12.2

Table 12.17 Time to first perceptible relief (TFPR) and Time to meaningful pain relief (TMRP). ITT population. N = XX

Parameter Treatment	Median	95% CI
Time to first perceptible relief (TFPR) hours		
OKITASK®	xx.x	[xx.x; xx.x]
PLACEBO	xx.x	[xx.x; xx.x]
Log rank test p-value	0.0000	
Time to meaningful pain relief (TMRP) hours		
OKITASK®	xx.x	[xx.x; xx.x]
PLACEBO	xx.x	[xx.x; xx.x]
Log rank test p-value	0.0000	

Table 12.18 Time to rescue medication (REMD). ITT population. N = XX

Parameter Treatment	Median	Median 95% CI ¹
Time to rescue medication (REMD) hours		
OKITASK®	xx.x	xx.x [xx.x; xx.x]
PLACEBO	xx.x	xx.x [xx.x; xx.x]
Log rank test p-value	0.0000	

Table 12.19 Overall assessment 6-hours post-dose. ITT population. N = XX

	OKITASK® N = XX	PLACEBO N = XX
(1) Very good	xx (xx.x%)	xx (xx.x%)
(2) Good	xx (xx.x%)	xx (xx.x%)
(3) Satisfactory	xx (xx.x%)	xx (xx.x%)
(4) Poor	xx (xx.x%)	xx (xx.x%)
(5) Very poor	xx (xx.x%)	xx (xx.x%)
No data ²	xx (xx.x%)	xx (xx.x%)
p-CMH		0.0000

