12.4 LISTINGS

Listing 12.1 Adverse events. Listing

Site-patient number	Gender	Age (years)	Treatment	AE number	AE description	MEDDRA System Organ Class	Preferred Term	Low Level Term	AE start date	AE start day of treatment	AE stop date	AE stop day of treatment	Relation to the study drug	Severity	Actions taken	Therapy due to AE	Outcome	Serious?
xx-xxxx	xx-xxxx	xx.x	XXXXXXX	1	xxxxxxxxxx	xxxxxxxxxx	xxxxxxxxxx	xxxxxxxxxx	xxxx-xx-xx	xx	xxxx-xx-xx	xx	xxxx	xxxx	xxxx	xx	xxxx	xxxx
xx-xxxx	xx-xxxx	xx.x	XXXXXXX	1	xxxxxxxxxx	xxxxxxxxxx	xxxxxxxxxx	xxxxxxxxxx	xxxx-xx-xx	xx	xxxx-xx-xx	xx	xxxx	xxxx	xxxx	xx	xxxx	xxxx

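### Section 11.2 of the SAP counts time periods from the consent date; read as written, this misplaces time to rescue medication and the adverse-event day of treatment, neither of which has an origin of its own

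*SAP*

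**What the plan says.** Section 11.2 consists of one sentence: "Calculation of time periods will be done relative to the date of the informed consent (IC"). No exception follows.

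Section 3.1 places consent first: "At Screening after signing the informed consent form, patient's demography, medical history and concomitant medications will be collected". It also gives the length of screening: "Screening procedures might take up to 4 days before the scheduled tooth extraction procedure including the actual day of extraction". Table 3.1 labels the period Day -4 to Day 1. Dosing takes place on Day 1, after extraction and randomization (sections 3.1, 3.2 and 3.4).

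For time to rescue, section 10.2 says: "Time to rescue medication will be calculated for each subject and presented using only median value". It adds a Kaplan-Meier curve and log-rank test if numbers allow, and names no start point. The row in Table 12.18 is headed "Time to rescue medication (REMD) hours".

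Listing 12.1 has a column "AE start day of treatment" and a matching stop-day column. Neither is defined.

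Other quantities do carry their own origin. The primary AUC runs from time 0. TFPR and TMPR come from stopwatches started at dosing. For adverse events, section 7.2 says: "Treatment emergency sign and symptom (TESS) will be AEs which started after the first study drug dose".

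**The concern.** Time to rescue medication is a named secondary objective (section 5.2). It is meant to show how long a single analgesic dose holds. Section 10.2 says the value is calculated and gives no origin, so anyone looking for one in the SAP finds the general rule in section 11.2. Followed literally, that rule makes each patient's value the sum of the post-dose time and an unrelated interval, the wait between consent and extraction. The median in Table 12.18 would then depend heavily on how early patients were screened. A day of treatment counted from consent would likewise not be a day of treatment.

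The rule also does not fit the output. It refers to a consent date, while Table 12.18 reports hours. Even for a patient who consents on Day 1, elapsed hours from a date are undefined unless someone chooses a clock time.

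**Working it through.** The plan states no figure on this point that could be reproduced. The check is date arithmetic, plus one illustration under assumed inputs.

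**Inputs from the SAP**
- Origin: consent date (section 11.2).
- Gap *d* from consent to dosing day: 0 to 3 days if the extraction day is one of the four screening days (section 3.1); up to 4 if Day -4 is read literally (Table 3.1).
- Window of interest: section 3.2 has "Should the patient require rescue medication at any time during 6 hours post-dose", so 0 to 6 h.
- Follow-up call: Day 3±1, 48 h after dosing (section 3.3).

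**1. Time to rescue.** Consent-based time = post-dose time + 24 × *d*. This treats the consent clock time as equal to the dosing clock time.

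| True time after dose | *d* = 0 | *d* = 1 | *d* = 3 | *d* = 4 |
|---|---|---|---|---|
| 1 h | 1 h | 25 h | 73 h | 97 h |
| 2 h | 2 h | 26 h | 74 h | 98 h |
| 6 h | 6 h | 30 h | 78 h | 102 h |

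The added interval reaches 72 h, which is 72/6 = 12 times the window, or 96 h, which is 96/6 = 16 times the window.

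**2. Date without a time.** If hours are counted from midnight of the consent date, the dosing clock time is added too. With dosing assumed at 09:00 or 15:00, rescue at 2 h becomes 2 + 9 = 11 h or 2 + 15 = 17 h when *d* = 0, and 83 h or 89 h when *d* = 3.

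**3. Adverse-event day.** With the dosing day as Day 1, an event on that day is Day 1 and an event at 48 h is Day 3, which matches section 3.3. With the consent day as Day 1, these become 1 + *d* and 3 + *d*: Days 4 and 6 for *d* = 3, Days 5 and 7 for *d* = 4.

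**4. Spread added (assumption).** The SAP does not give the distribution of *d*. If it were uniform on 0, 1, 2 and 3 days, the offset SD would be 24 × √1.25 = 26.8 h, about 26.8/6 = 4.5 times the window. Had every patient the same gap, the added SD would be zero and only the median would shift.

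**5. Effect on the log-rank test (assumption).** Simulated inputs, none from the SAP: exponential times to rescue with medians 2 h and 5 h, censoring at 6 h, whole-day gaps uniform and independent of arm, two-sided 5% test, 1,000 trials per setting. The 35 patients per arm is the planned enrolment.

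| Gap range | Power, dose origin | Power, consent origin |
|---|---|---|
| 0–3 days | 0.89 | 0.60 |
| 0–4 days | 0.91 | 0.54 |

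The small difference within the dose-origin column is simulation error. The table shows direction and rough order of loss only.

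**The case against.** The strongest reply is that nobody would apply section 11.2 this way. The SAP puts rescue on a post-dose clock throughout: section 3.2, section 4 and the footnotes to Table 3.1 all speak of hours after the dose, and one footnote says time to rescue will be recorded. The visit scale is tied to the dosing day, and a footnote in section 9.2 sets baseline at Day 1, time 0 minutes. A rule stated in dates looks like a convention for age or duration of history. The protocol, which was not available for this review, may also define the endpoint, so the silence of section 10.2 alone would be no defect.

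Much of this stands. A dose origin was very probably intended, and a careful programmer would question a 74 h rescue time in a 6 h window. But intent is not a written exception. Section 10.2 says the value is calculated, and no passage takes time to rescue or the adverse-event day out of section 11.2. The defect is an unqualified rule that conflicts with the plan's own outputs, not merely a missing detail.

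The limits on harm also stand:
- Time to rescue is one of several secondary endpoints. Its log-rank test is conditional on adequate numbers.
- Listing 12.1 also prints adverse-event start and stop dates, and no adverse-event summary table in section 12 uses day of treatment.

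A reader might infer from the breadth of section 11.2 that every timed result is corrupted, the primary analysis included. The documents do not support that, because AUC, TFPR, TMPR and TESS have dose-based definitions. Nor do they support a bias between arms. The consent-to-dose gap is fixed before randomization, so it adds noise and weakens the comparison but does not systematically favour a treatment.

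**Conclusion.** The point holds, at moderate severity. As written, section 11.2 governs time to rescue medication and the two day-of-treatment columns in Listing 12.1. It would add 0 to 72 h, or up to 96 h on the literal Day -4 reading, to an endpoint observed over 6 h. It also rests an endpoint in hours on a calendar date. The medians would be distorted and a log-rank comparison diluted.

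The range of the added interval follows from the SAP alone. The 26.8 h SD and the power figures depend on assumed consent gaps, and the power figures on assumed rescue times as well; they are illustrations, not estimates for this trial. The conclusion also assumes that no other governing text, such as the protocol, supplies a dose origin. Even if it does, section 11.2 should be corrected, because it would then contradict that text.

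**What to change.** Three wording changes to the SAP before database lock:

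1. **Section 11.2:** limit the consent date to pre-treatment quantities, for example age or duration of medical history.
2. **Section 10.2:** state that time to REMD equals the date and time of rescue medication minus the date and time of study drug administration, in hours.
3. **Listing 12.1:** define adverse-event start and stop day with the dosing day as Day 1. If an adverse-event duration is reported, it should run from event start to event stop, not from dosing.

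The sample size, the primary analysis and the populations do not change. One item needs confirming: the SAP does not expressly say that the clock time of dosing is captured. The actual-time AUC from time 0 and the stopwatches started at dosing imply that it is available. If it is not on the eCRF, the recorded time of the VAS taken immediately before dosing (section 3.2) could serve as the origin, provided the SAP says so.

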12. TABLE EXAMPLES¹

Table 12.1 Disposition

	OKITASK® N = XX	PLACEBO N = XX
Screened		xx
Safety population	xx (xx.x%)	xx (xx.x%)
Intent-to-treat (ITT) population	xx (xx.x%)	xx (xx.x%)
Per-Protocol (PP) population	xx (xx.x%)	xx (xx.x%)
Study completion	xx (xx.x%)	xx (xx.x%)
Early termination	xx (xx.x%)	xx (xx.x%)
Adverse event	xx (xx.x%)	xx (xx.x%)
Death	xx (xx.x%)	xx (xx.x%)
Patient required rescue medication	xx (xx.x%)	xx (xx.x%)
Lost to follow-up	xx (xx.x%)	xx (xx.x%)
Consent withdrawn	xx (xx.x%)	xx (xx.x%)
Investigator decision	xx (xx.x%)	xx (xx.x%)
Protocol violation, including non-compliance	xx (xx.x%)	xx (xx.x%)
Patient required prohibited medications		
Protocol entry criteria not met	xx (xx.x%)	xx (xx.x%)
The patient starts of another study drug	xx (xx.x%)	xx (xx.x%)
Study is stopped by Sponsor decision	xx (xx.x%)	xx (xx.x%)
Study is stopped by regulatory instance / ethics committee	xx (xx.x%)	xx (xx.x%)
Pregnancy	xx (xx.x%)	xx (xx.x%)
Other	xx (xx.x%)	xx (xx.x%)

12.1 BASELINE AND DEMOGRAPHY

Table 12.2 Demographics. Screening (Day -4 to Day 1). ITT population. N = XX

Parameter	OKITASK® N = XX	PLACEBO N = XX
Age (years)		
N	xx	xx
Mean (SD)	xx.x (xx.x)	xx.x (xx.x)
Median	xx.x	xx.x
Min; Max	xx.x; xx.x	xx.x; xx.x
p-value ANOVA	0.****	
Gender		
Male	xx (xx.x%)	xx (xx.x%)
Female	xx (xx.x%)	xx (xx.x%)
No data ²	xx (xx.x%)	xx (xx.x%)
p-value χ^2 or Fisher	0.****	
Race		
No data ³	xx (xx.x%)	xx (xx.x%)
Caucasian	xx (xx.x%)	xx (xx.x%)
Other	xx (xx.x%)	xx (xx.x%)
Height (cm)		
N	xx	xx
Mean (SD)	xx.x (xx.x)	xx.x (xx.x)
Median	xx.x	xx.x
Min; Max	xx.x - xx.x	xx.x - xx.x
Weight (kg)		
N	xx	xx
Mean (SD)	xx.x (xx.x)	xx.x (xx.x)
Median	xx.x	xx.x
Min; Max	xx.x - xx.x	xx.x - xx.x
BMI (kg/m²)		

¹ Tables in the statistical report could be differ from these examples but all necessary information will be presented

² if any

³ if any

Parameter	OKITASK® N = XX	PLACEBO N = XX
N	xx	xx
Mean (SD)	xx.x (xx.x)	xx.x (xx.x)
Median	xx.x	xx.x
Min; Max	xx.x - xx.x	xx.x - xx.x

**Table 12.3 Medical history. Screening (Day -4 to Day 1).
ITT population. N = XX**

System Organ Class term Preferred term	OKITASK® N = XX	PLACEBO N = XX
Total patients	xx (xx.x%)	xx (xx.x%)
SOC term	xx (xx.x%)	xx (xx.x%)
Preferred term 1	xx (xx.x%)	xx (xx.x%)
Preferred term 2	xx (xx.x%)	xx (xx.x%)
...		

**Table 12.4 Concomitant¹ diseases. Screening (Day -4 to Day 1).
ITT population. N = XX**

Similar

**Table 12.5 Previous therapy. Screening (Day -4 to Day 1).
ITT population. N = XX**

ATC Group Drug (ATC code)	OKITASK® N = XX	PLACEBO N = XX
ATC Group (level 3)	xx (xx.x%)	xx (xx.x%)
Drug 1 (ATC level 5)	xx (xx.x%)	xx (xx.x%)
Drug 2 (ATC level 5)	xx (xx.x%)	xx (xx.x%)
...		

**Table 12.6 Pregnancy test. Screening (Day -4 to Day 1). Females.
ITT population. N = XX**

	OKITASK® N = XX	PLACEBO N = XX
Positive	xx (xx.x%)	xx (xx.x%)
Negative	xx (xx.x%)	xx (xx.x%)
Not applicable	xx (xx.x%)	xx (xx.x%)
No data ²	xx (xx.x%)	xx (xx.x%)

**Table 12.7 Oral cavity examination. Screening (Day -4 to Day 1).
ITT population. N = XX**

CS ³ Abnormalities only ⁴	OKITASK® N = XX	PLACEBO N = XX
General appearance	xx (xx.x%)	xx (xx.x%)
Condition of mucous membranes	xx (xx.x%)	xx (xx.x%)
Teeth	xx (xx.x%)	xx (xx.x%)
Throat	xx (xx.x%)	xx (xx.x%)

¹ Flag “ongoing” is set

² if any

³ Clinically significant

⁴ Parameters with normal values or NCS (not clinically significant) in both groups should be omitted from this table

Table 12.8 Vital signs. Screening (Day -4 to Day 1). ITT population. N = XX

CS ¹ Abnormalities only ²	OKITASK [®] N = XX	PLACEBO N = XX
Pulse rate (beats/min)	xx (xx.x%)	xx (xx.x%)
Respiratory rate (/min)	xx (xx.x%)	xx (xx.x%)
Systolic blood pressure (mm Hg)	xx (xx.x%)	xx (xx.x%)
Diastolic blood pressure (mm Hg)	xx (xx.x%)	xx (xx.x%)
Body temperature (oral cavity) (°C)	xx (xx.x%)	xx (xx.x%)

12.2 EFFICACY

12.2.1 Primary efficacy

Table 12.9 Primary efficacy. Visual Analogue Scale. Pain Intensity Assessment with LOCF. ITT population. N = XX

Parameter Treatment	Result				
	N	Mean (SD)	Median	Min	Max
Visual Analogue Scale. Pain Intensity. AUC_{0-6h}. LOCF					
OKITASK [®]	XX	xx.x (xx.x)	xx.x	xx.x	xx.x
PLACEBO	XX	xx.x (xx.x)	xx.x	xx.x	xx.x
p-value ANOVA = 0.***					
Visual Analogue Scale. Pain Intensity. AUC_{0-6h}. Multiple Imputation					
OKITASK [®]	XX	xx.x (xx.x)	xx.x	xx.x	xx.x
PLACEBO	XX	xx.x (xx.x)	xx.x	xx.x	xx.x
p-value ANOVA = 0.***					

Table 12.10 Primary efficacy. Visual Analogue Scale. Pain Intensity Assessment without LOCF. PP population. N = XX

Parameter Treatment	Result				
	N	Mean (SD)	Median	Min	Max
Visual Analogue Scale. Pain Intensity. AUC_{0-6h}					
OKITASK [®]	XX	xx.x (xx.x)	xx.x	xx.x	xx.x
PLACEBO	XX	xx.x (xx.x)	xx.x	xx.x	xx.x
p-value ANOVA = 0.***					

Table 12.11 Primary efficacy. Visual Analogue Scale. Pain Intensity Assessment with LOCF. ITT population. N = XX

Parameter Treatment	Result				
	N	Mean (SD)	Median	Min	Max
Visual Analogue Scale. Pain Intensity. AUC_{0-6h}. LOCF					
OKITASK [®]	XX	xx.x (xx.x)	xx.x	xx.x	xx.x
PLACEBO	XX	xx.x (xx.x)	xx.x	xx.x	xx.x
p-value ANOVA = 0.***					
Visual Analogue Scale. Pain Intensity. AUC_{0-6h}. Multiple Imputation					
OKITASK [®]	XX	xx.x (xx.x)	xx.x	xx.x	xx.x
PLACEBO	XX	xx.x (xx.x)	xx.x	xx.x	xx.x

¹ Clinically significant² Parameters with normal values or NCS (not clinically significant) in both groups should be omitted from this table

Parameter Treatment	Result				
	N	Mean (SD)	Median	Min	Max
p-value ANOVA = 0.***					

Table 12.12 Primary efficacy. Visual Analogue Scale. Pain Intensity Assessment without LOCF. PP population. N = XX

Parameter Treatment	Result				
	N	Mean (SD)	Median	Min	Max
Visual Analogue Scale. Pain Intensity. AUC_{0-6h}					
OKITASK [®]	XX	XX.X (XX.X)	XX.X	XX.X	XX.X
PLACEBO	XX	XX.X (XX.X)	XX.X	XX.X	XX.X
p-value ANOVA = 0.***					

12.2.2 Secondary efficacy

Table 12.13 secondary efficacy. Visual Analogue Scale. Pain Intensity Assessment with LOCF. ITT population. N = XX

Parameter Treatment	Result				
	N	Mean (SD)	Median	Min	Max
Visual Analogue Scale. Pain Intensity. AUC_{0-6h}. LOCF					
OKITASK [®]	XX	XX.X (XX.X)	XX.X	XX.X	XX.X
PLACEBO	XX	XX.X (XX.X)	XX.X	XX.X	XX.X
p-value ANOVA = 0.***					
Visual Analogue Scale. Pain Intensity. AUC_{0-6h}. Multiple Imputation					
OKITASK [®]	XX	XX.X (XX.X)	XX.X	XX.X	XX.X
PLACEBO	XX	XX.X (XX.X)	XX.X	XX.X	XX.X
p-value ANOVA = 0.***					

Table 12.14 secondary efficacy. Visual Analogue Scale. Pain Intensity Assessment with LOCF. ITT population. N = XX

Parameter Treatment	Result				
	N	Mean (SD)	Median	Min	Max
Visual Analogue Scale. Pain Intensity. AUC_{0-6h}. LOCF					
OKITASK [®]	XX	XX.X (XX.X)	XX.X	XX.X	XX.X
PLACEBO	XX	XX.X (XX.X)	XX.X	XX.X	XX.X
p-value ANOVA = 0.***					
Visual Analogue Scale. Pain Intensity. AUC_{0-6h}. Multiple Imputation					
OKITASK [®]	XX	XX.X (XX.X)	XX.X	XX.X	XX.X
PLACEBO	XX	XX.X (XX.X)	XX.X	XX.X	XX.X
p-value ANOVA = 0.***					

Table 12.15 Secondary efficacy. Visual Analogue Scale. Pain Intensity profile. ITT population. N = XX

Parameter Treatment	Day 1 time	Results				
		N	Mean (SD)	Median	Min	Max

Parameter Treatment	Day 1 time	Results				
		N	Mean (SD)	Median	Min	Max
Visual Analog Scale. Pain intensity						
OKITASK®	0 min. Baseline	xx	xx.x (xx.x)	xx.x	xx.x	xx.x
PLACEBO	0 min. Baseline	xx	xx.x (xx.x)	xx.x	xx.x	xx.x
$\mu_T - \mu_R$ 95% CI			xx.x [xx.x; xx.x]			
OKITASK®	5 minutes	xx	xx.x (xx.x)	xx.x	xx.x	xx.x
PLACEBO	5 minutes	xx	xx.x (xx.x)	xx.x	xx.x	xx.x
$\mu_T - \mu_R$ 95% CI			xx.x [xx.x; xx.x]			
...						
OKITASK®	6 hours	xx	xx.x (xx.x)	xx.x	xx.x	xx.x
PLACEBO	6 hours	xx	xx.x (xx.x)	xx.x	xx.x	xx.x
$\mu_T - \mu_R$ 95% CI			xx.x [xx.x; xx.x]			

Figure 12.1 Secondary efficacy. Visual Analogue Scale. Pain Intensity profile. ITT population. N = XX

[figure not shown]

Figure 12.2 Secondary efficacy. Visual Analogue Scale. Difference in Pain Intensity means with 95% CI. ITT population. N = XX

[figure not shown]

Table 12.16 Secondary efficacy. Visual Analogue Scale. Pain Relief profile. ITT population. N = XX

Parameter	Treatment	Day 1 time	Results				
			N	Mean (SD)	Median	Min	Max
Visual Analog Scale. Pain relief							
OKITASK [®]	0 min. Baseline	xx	xx.x (xx.x)	xx.x	xx.x	xx.x	xx.x
PLACEBO	0 min. Baseline	xx	xx.x (xx.x)	xx.x	xx.x	xx.x	xx.x
$\mu_T - \mu_R$	95% CI		xx.x [xx.x; xx.x]				
OKITASK [®]	5 minutes	xx	xx.x (xx.x)	xx.x	xx.x	xx.x	xx.x
PLACEBO	5 minutes	xx	xx.x (xx.x)	xx.x	xx.x	xx.x	xx.x
$\mu_T - \mu_R$	95% CI		xx.x [xx.x; xx.x]				
...							
OKITASK [®]	6 hours	xx	xx.x (xx.x)	xx.x	xx.x	xx.x	xx.x
PLACEBO	6 hours	xx	xx.x (xx.x)	xx.x	xx.x	xx.x	xx.x
$\mu_T - \mu_R$	95% CI		xx.x [xx.x; xx.x]				

Figure 12.3 Secondary efficacy. Visual Analogue Scale. Pain Relief profile. ITT population. N = XX

Similar to Figure 12.1

Figure 12.4 Secondary efficacy. Visual Analogue Scale. Difference in Pain Relief means with 95% CI. ITT population. N = XX

Similar to Figure 12.2

Table 12.17 Time to first perceptible relief (TFPR) and Time to meaningful pain relief (TMRP). ITT population. N = XX

Parameter Treatment	Median	95% CI
Time to first perceptible relief (TFPR) hours		
OKITASK®	xx.x	[xx.x; xx.x]
PLACEBO	xx.x	[xx.x; xx.x]
Log rank test p-value	0.0000	
Time to meaningful pain relief (TMRP) hours		
OKITASK®	xx.x	[xx.x; xx.x]
PLACEBO	xx.x	[xx.x; xx.x]
Log rank test p-value	0.0000	

Table 12.18 Time to rescue medication (REMD). ITT population. N = XX

Parameter Treatment	Median	Median 95% CI ¹
Time to rescue medication (REMD) hours		
OKITASK®	xx.x	xx.x [xx.x; xx.x]
PLACEBO	xx.x	xx.x [xx.x; xx.x]
Log rank test p-value	0.0000	

Table 12.19 Overall assessment 6-hours post-dose. ITT population. N = XX

	OKITASK® N = XX	PLACEBO N = XX
(1) Very good	xx (xx.x%)	xx (xx.x%)
(2) Good	xx (xx.x%)	xx (xx.x%)
(3) Satisfactory	xx (xx.x%)	xx (xx.x%)
(4) Poor	xx (xx.x%)	xx (xx.x%)
(5) Very poor	xx (xx.x%)	xx (xx.x%)
No data ²	xx (xx.x%)	xx (xx.x%)
p-CMH		0.0000

